5.3 MISSING DATA HANDLING

General Considerations: Subjects lost to follow-up (or who dropped out) will be included in statistical analyses up to the point of their last evaluation.

Duration of Response and Progression-free Survival: Data for subjects without disease progression or death will be censored at the date of the last tumor assessment and before the initiation of alternative anticancer therapy.

Safety: Missing or partial start and end dates for AEs and concomitant medications will be imputed according to prespecified, conservative imputation rules. No other imputation of values for missing data will be performed.

5.4 DETERMINATION OF SAMPLE SIZE

No formal statistical tests of hypotheses will be performed. Descriptive statistics (including means, standard deviations, and medians for continuous variables and proportions for discrete variables) will be used to summarize data as appropriate.

The trial design is specified because of its practical simplicity, use of a biomarker, and not because of power considerations. The sample size of 20 subjects in a Phase 1b study is considered adequate to evaluate the initial safety, PK/PD, and activity of *acalabrutinib* in this patient population.

5.5 DATA ANALYSIS

5.5.1 Safety Parameters

Safety summaries will include summaries in the form of tables and listings. The frequency (number and percentage) of treatment emergent AEs will be reported in each treatment group by MedDRA System Organ Class and Preferred Term. Summaries will also be presented by the severity of the AE (per CTCAE, v4.03) and by relationship to study drug.

Laboratory shift tables containing counts and percentages will be prepared by treatment assignment, laboratory parameter, and time. Summary tables will be prepared for each laboratory parameter. Figures of changes in laboratory parameters over time will be generated.

Results of vital sign assessments, ECGs, and physical exams will be tabulated and summarized.

5.5.2 Demographics and Baseline Characteristics

Additional analyses will include summaries of subject demographics, baseline characteristics, compliance, and concurrent treatments. Concomitant medications will be coded according to the World Health Organization (WHO) Drug Dictionary and tabulated.

5.5.3 Study Treatment Administration and Compliance

Descriptive information will be provided regarding the number of *acalabrutinib* doses prescribed, the total number of doses taken, the number of days of treatment, and the number and timing of prescribed dose reductions and interruptions.

For each patient, *acalabrutinib* compliance will be described in terms of the proportion of study drug actually taken based on returned pill count relative to the amount that was dispensed (taking into account physician-prescribed modifications and interruptions).

5.5.4 Analysis of Efficacy Parameters

Response Rate

The individual and composite endpoints of response and progression will be determined. Tumor control will be documented at each assessment by response category (eg, CR, PR, SD, PD) as defined for each response parameter, date that response is first documented, and date of DLBCL disease progression.

Overall response rate will be defined as the proportion of subjects who achieve a CR or PR. Overall response rate will be calculated and the corresponding 97.5% one-sided confidence interval will be derived.

Duration of Response

The duration of response (DOR) defined as the interval from the first documentation of CR or PR to the earlier of the first documentation of definitive disease progression or death from any cause. Kaplan-Meier methods will be used to estimate event-free curves and corresponding quantiles (including the median). Data from surviving, nonprogressing subjects will be censored at the earliest of the time of initiation of anticancer treatment other than the study treatment or the last time that lack of definitive DLBCL progression was objectively documented. Data from subjects who have DLBCL progression or die after ≥ 2 consecutive missing tumor assessments will be censored at the last time before the missing assessments that lack of DLBCL progression was objectively documented.

Progression-free Survival

Progression-free survival (PFS) is defined as the interval from the start of acalabrutinib therapy to the earlier of the first documentation of objective DLBCL disease progression or death from any cause. Kaplan-Meier methods will be used to estimate the event-free curves and corresponding quantiles (including the median). Data from surviving, non-progressing subjects will be censored at the earliest of the time of initiation of anticancer treatment other than the study treatment or the last time that lack of DLBCL progression was objectively documented. Data from subjects who have DLBCL progression or die after ≥ 2 consecutive missing tumor assessments will be censored at the

last time prior to the missing assessments that lack of FL progression was objectively documented.

Time-to-Next Treatment

Time-to-next treatment defined as the time from start of *acalabrutinib* therapy for DLBCL on this protocol to the start of the next treatment for DLBCL. Kaplan-Meier methods will be used to estimate the event-free curves and corresponding quantiles (including the median). Data from subjects who have not received subsequent therapy for DLBCL will be censored at the earliest of death or the last time that lack of administration of a new therapy for DLBCL was objectively documented.

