3.0 STUDY DESIGN

3.1 DESCRIPTION OF STUDY

This study is a multicenter and open-label study. Twenty subjects, 10 relapsed and 10 refractory, will be enrolled and will take 100 mg of *acalabrutinib* BID. The study will be conducted at approximately 9 sites in up to 4 countries.

Relapsed subjects will be defined as subjects who have had a PR or better ([Cheson 2014](#) or [Cheson 2007](#) criteria) from the previous anticancer therapy and now have progressed. Refractory subjects will be defined as subjects whose best response to the previous anticancer therapy was SD or did not respond to therapy.

Treatment with *acalabrutinib* may be continued for > 28 days until disease progression or an unacceptable drug-related toxicity occurs. Tumor assessments will be performed at 8- to 12-week intervals during the trial. Dose modification provisions are provided in

[Section 3.5.5](#). Note: temporary withholding of study drug for as little as 7 days can cause a transient worsening of disease and/or of constitutional symptoms. Refer to [Section 3.8](#) for more information on assessing disease progression under these circumstances. All subjects who discontinue study drug will have a safety follow-up visit 30 (± 7) days after the last dose of study drug unless they have started another cancer therapy within that timeframe.

All subjects will have hematology, chemistry, and urinalysis safety panels done at screening. Once dosing commences (Day 1), all subjects will be evaluated for safety, including serum chemistry and hematology, once weekly for the first 4 weeks, every 2 weeks in Cycle 2 and monthly thereafter. PK/PD testing will be done in Cycle 1 and Cycle 2.

Refer to [Appendix 4](#) for a comprehensive list of study assessments and their timing. Subjects showing clinical benefit and who are tolerating *acalabrutinib* may remain on study through the end of Cycle 12. The end of trial is defined as the point when the last subject enrolled completes the end of Cycle 12 or withdraws for any reason and completes the 30-day follow-up visit (if applicable), whichever occurs first.

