4.4 TIME-TO-NEXT TREATMENT

Subjects who discontinue study therapy will continue on study for follow-up of safety ([Section 4.3](#)) and time-to-next DLBCL therapy unless they withdraw consent for further follow-up. Thus, all subjects receiving ≥ 1 dose of study drug will be followed during the immediate post-therapy and long-term follow-up assessments unless the subject withdraws consent for such follow-up to be conducted. The date the subject is withdrawn from the study and the reason for discontinuation will be recorded and also should be described on the appropriate electronic case report form (eCRF).

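### New anticancer therapy censors PFS and DOR only in subjects who never progress or die, so whether a subject who switches treatment is censored depends on the later outcome

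*Protocol*

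**What the plan says.** Four statements in the protocol decide how a subject who changes treatment is handled.

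- **Event definitions (5.5.4).** PFS runs to the "earlier of the first documentation of objective DLBCL disease progression or death from any cause". DOR runs to the "earlier of the first documentation of definitive disease progression or death from any cause". Neither is limited to the time before new therapy.
- **New-therapy censoring (5.5.4).** The DOR paragraph says "Data from surviving, nonprogressing subjects will be censored at the earliest of the time of initiation of anticancer treatment" other than study treatment, or at the last objective documentation of no progression. The PFS paragraph has the same rule.
- **Missing-data section (5.3).** "Data for subjects without disease progression or death will be censored at the date of the last tumor assessment" and before alternative therapy begins. The restriction to subjects without an event is repeated.
- **Censoring of subjects who do have an event (5.5.4).** "Data from subjects who have DLBCL progression or die after ≥ 2 consecutive missing tumor assessments will be censored" at the last assessment before the gap. Missed assessments are the only trigger. New therapy is not named.

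**The concern.** The new-therapy rule is conditioned on something known only afterwards: whether the subject went on to progress or die. Two subjects with the same history up to the switch are treated differently. The one who fails contributes the time on the other drug and an event. The one who does not is removed from the risk set at the switch or the last assessment.

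Kaplan-Meier estimation assumes that censoring carries no information about the later outcome, and here the later outcome determines the censoring. The curve then estimates neither PFS with switchers censored nor PFS regardless of later therapy, and some failures on another drug are attributed to acalabrutinib. DOR has the same fault for responders who move to other treatment. With 20 subjects, one or two such records shift the curve visibly.

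**Working it through.** The protocol states no PFS or DOR figure, and N = 20 does not come from a power calculation (5.4), so there is no figure to reproduce. The check has three parts.

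**1. One subject, two outcomes.** Scans fall at the end of Cycles 2, 4 and 6 and then every 3 cycles (4.1.20), that is, at weeks 8, 16, 24, 36 and 48. Suppose stable disease at week 8, drug stopped at week 9 and chemotherapy started at week 10.
- Death at week 20: only the week 16 scan has been missed, so the two-missed-assessments rule does not apply. PFS is an event at 20 weeks.
- Alive without progression: PFS is censored at the earlier of week 10 and week 8, that is, week 8.

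The missed-assessment rule removes later failures only. With intervals of 8 to 12 weeks (3.1), two intervals are 16 to 24 weeks from the last scan.

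**2. Twenty subjects, by hand (all counts assumed).** On acalabrutinib, 8 events at month 2, 3 at month 4 and 1 at month 6; 4 event-free to month 11. Four more subjects switch at month 2.5, which is also taken as their last assessment, and two of them fail at month 4. After month 2, S = 12/20 = 0.60 under every rule. Then:

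| Rule | Month 4 | Month 6 |
|---|---|---|
| As written (2 censored at 2.5; 10 at risk, 5 events) | 0.60 × 5/10 = 0.30 | 0.30 × 4/5 = 0.24 |
| Censor all 4 switchers (8 at risk, 3 events) | 0.60 × 5/8 = 0.375 | 0.375 × 4/5 = 0.30 |
| Ignore the switch (12 at risk, 5 events) | 0.60 × 7/12 = 0.35 | 0.35 × 6/7 = 0.30 |

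The two consistent rules agree at 30% at month 6. The written rule gives 24%.

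**3. Simulation on the protocol's scan dates.** Assumptions: exponential PFS with median 12, 20 or 28 weeks; about 8-30% of subjects switching before failure; hazard ratio 0.5-1.0 after the switch; follow-up to 52 weeks; two-missed-assessments rule applied; every later progression and death known.

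For median 20 weeks, 28% switching and hazard ratio 1.0:

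| Rule | 24-week PFS | Median (weeks) |
|---|---|---|
| (a) As written | 38.4% | 17.6 |
| (b) Censor all switchers at the last prior scan | 41.5% | 18.9 |
| (c) Count all later events | 43.5% | 20.0 |

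Rule (c) agrees with the true value, 2^(−24/20) = 43.5%. The cost of outcome-dependent censoring is (b) − (a) = 3.1 points. The remaining (c) − (b) = 2.0 points comes from dating censoring back to the last scan.

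Across the assumed range, (b) − (a) is about 0.5 to 3.5 points at 24 weeks and up to 1.7 weeks in the median. Between 15% and 53% of switchers are counted as events on another therapy.

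A simpler model censors at the switch itself and replaces the scan rule with a flat 3.7-month window. It can give larger gaps: 19.7% against 24.9% at 6 months for a 3-month median, 30% chance of switching and equal hazard. With a 6-month median and hazard ratio 2 it gives 44.2% against 50.0%. It does not use the protocol's scan dates.

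**The case against.** **Capture of later events.** The simulation assumes that all failures after the switch are known. Section 4.4 keeps subjects on study ("Subjects who discontinue study therapy will continue on study for follow-up of safety" and time to next therapy), but Appendix 4 marks no tumor assessment at early termination, safety follow-up or long-term follow-up. The 30-day visit is waived once another therapy starts (4.3), and routine adverse event reporting ends at that point (6.2.1). This stands: the sizes above are upper bounds. It does not remove the asymmetry, because a death or progression that does become known is still counted.

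**Size.** At N = 20 the standard error of a 43.5% estimate is √(0.435 × 0.565 / 20) ≈ 11 points, and these are descriptive secondary endpoints. The switching rates have no source in the protocol. This also stands, and is why the effect is called modest.

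**Intent.** The restriction might have been meant as status when new therapy starts. The text does not say so, and the separate sentence for subjects who progress or die, together with 5.3, points to the literal reading. If two programmers can read it differently, it still needs rewording.

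**Stronger readings that a reader might infer, and that do not hold.**
- *The written curve is always below both alternatives.* It is not: time kept on the other drug also enlarges the risk set. In the simpler model without any missed-assessment cut-off (true median 3 months, hazard ratio 0.5, 30% chance of switching), the written rule gave a median of 3.07 months against 3.00 with all switchers censored.
- *The full gap to a count-all-events analysis, about 1.5 to 11 points, is due to this fault.* Part of it is backdating to the last scan, which the fix retains: 2.0 of the 5.1 points in the example above.
- *Sections 5.3 and 5.5.4 conflict on the censoring date.* Section 5.5.4 takes the earliest of the two dates, so both sections give the last scan unless a progression-free scan follows the switch. None is scheduled after discontinuation.

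**Conclusion.** The rule is wrong as written. In both 5.5.4 and 5.3, a subject who switches treatment before documented progression is censored or counted as an event according to what happens later, and the resulting Kaplan-Meier estimate corresponds to neither consistent analysis. This follows from the text alone.

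The size rests on assumptions: about 8-30% switching, hazard ratio 0.5-1.0 afterwards and full capture of later events. On the protocol's scan dates these give a 24-week PFS about 0.5-3.5 points below that obtained by censoring every switcher. The direction is generally, not invariably, downward, and a worse prognosis after the switch would widen the gap. The same wording affects DOR, for which no separate size was computed. The fault should be corrected, but it does not threaten the primary safety objective.

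**What to change.** In 5.3 and in both the PFS and DOR paragraphs of 5.5.4, replace the restricted rule with one sentence:

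*Any subject who starts anticancer treatment other than study treatment before documented progression or death is censored at the last tumor assessment before that start, whatever happens afterwards.*

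Keep the two-missed-assessments rule alongside it. Optionally add a sensitivity analysis that counts all later progressions and deaths regardless of new therapy, noting that follow-up after the switch is incomplete.

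The cost is wording in two sections and no new data. The downside is that a few events on other therapy become censored observations, in a study with few events to begin with.

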1.0 BACKGROUND INFORMATION

1.1 DIFFUSE LARGE B-CELL LYMPHOMA

Diffuse large B-cell lymphoma (DLBCL) is the most common of the aggressive NHL in the United States, with an annual incidence that has been rising gradually since the 1990s. While approximately half of the incremental rise in incidence of DLBCL is attributable to identifiable factors—such as the increase in the incidence of HIV-related DLBCL, the evolution of more specific diagnostic techniques, and revisions in lymphoma classification schemes—much of the rising incidence remains unexplained. A very aggressive malignancy in its untreated natural history, DLBCL is a potentially curable disease, with a significant proportion of patients cured with modern standard chemoimmunotherapy. Nonetheless, for those patients not cured by standard initial therapy, the prognosis remains generally poor, and DLBCL still accounts for the highest number of deaths per year of all the NHL histologies.

Treatment for DLBCL

Anthracycline-based combination chemotherapy, eg, CHOP (cyclophosphamide, doxorubicin, vincristine, and prednisolone), has been the standard approach to initial therapy for DLBCL for decades. While several variants to the CHOP regimen have been developed, often varying by the addition of other agents or dose-intensification of the agents, a large multi-arm Phase 3 trial demonstrated no differences in disease-free or overall survival (OS) with these “second-generation” variants as compared with CHOP (Fisher 1993). The addition of rituximab to CHOP (R-CHOP) or CHOP-like regimens, however, has resulted in improvement in both disease-free and OS in DLBCL in 3 large randomized Phase 3 trials (Coiffier 2002, Habermann 2006, Pfreundschuh 2006). Long-term follow-up of the GELA LNH-98.5 study confirmed that a greater proportion of patients are cured using R-CHOP compared with CHOP alone (Coiffier 2010).

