2.0 STUDY OBJECTIVES

2.1 PRIMARY OBJECTIVE

To characterize the safety profile of *acalabrutinib* in subjects with relapsed or refractory ABC DLBCL

2.2 SECONDARY OBJECTIVES:

- To characterize the PK of *acalabrutinib*
- To evaluate the PD effects of *acalabrutinib*
- To evaluate the activity of *acalabrutinib* as measured by response rate, duration of response, time-to-next treatment, and progression-free survival

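### Time-to-next treatment is a Kaplan-Meier analysis that censors at death, so its curve gives neither the proportion alive without new therapy nor, by its complement, the proportion who start it

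*Protocol*

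**What the plan says.** Section 5.5.4 (Time-to-Next Treatment) measures from the start of acalabrutinib "therapy for DLBCL on this protocol to the start of the next treatment for DLBCL". It asks for Kaplan-Meier event-free curves and quantiles, the median among them. On subjects without further therapy it states: "Data from subjects who have not received subsequent therapy for DLBCL will be censored at the earliest of death or the last time"; the second date is the latest one on which it was confirmed that no new therapy had begun. Cause of death is not distinguished, and no competing-risk estimate is named.

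The same section handles death differently for the neighbouring endpoints. PFS runs "to the earlier of the first documentation of objective DLBCL disease progression or death from any cause", and duration of response also ends at death from any cause.

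Section 2.2 makes TTNT one of four measures of activity: "as measured by response rate, duration of response, time-to-next treatment, and progression-free survival". Section 1.1 says of the population that "for those patients not cured by standard initial therapy, the prognosis remains generally poor". Section 3.1 sets the size: "Twenty subjects, 10 relapsed and 10 refractory, will be enrolled".

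**The concern.** A subject who deteriorates and dies before any further lymphoma treatment is a failure for PFS but a censored observation for TTNT. Kaplan-Meier handles a censored subject as if the later chance of the event were the same as for those still under observation. That cannot hold after death, and it is doubtful even as an approximation when the lymphoma drives both the death and the need for treatment.

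At stake is how a reported activity measure will be read. An event-free curve with a median invites the reading of time alive without needing another treatment. Under the written rule it is not that, and its complement is not the proportion who went on to further therapy.

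**Working it through.** The protocol states no expected TTNT median, death rate or precision, so there is no figure of its own to reproduce. The check is whether the rule has the described effect, and how large it could be.

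**Direction, without a model.** At each therapy start the Kaplan-Meier curve is multiplied by (1 - 1/n), with n the number at risk. The curve for alive without new therapy takes the same factors plus one for each death, so it lies at or below the Kaplan-Meier curve. The cumulative incidence of next therapy rises at each start by 1/n times the alive-and-untreated curve just before it. 1 minus Kaplan-Meier rises by 1/n times the higher Kaplan-Meier curve. It therefore lies at or above the cumulative incidence, and strictly above it from the first therapy start that follows a death.

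**Size when deaths replace therapy starts.** Assume constant hazards a (next therapy) and b (death first), with total h = a + b held fixed and d = b/h.

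- Reported median: ln2/a = ln2/[h(1-d)]
- Median to next therapy or death: ln2/h
- Ratio: 1/(1-d), whatever the value of h

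With an assumed composite median of 3 months (h = ln2/3), at 6 months:

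- alive without new therapy = 2^(-2) = 25%
- Kaplan-Meier = 2^(-2(1-d))
- cumulative incidence of next therapy = (1-d) x 75%

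| d (assumed) | Ratio | Reported median (months) | Kaplan-Meier at 6 months | Alive without new therapy | 1 - Kaplan-Meier | Cumulative incidence |
|---|---|---|---|---|---|---|
| 20% | 1.25 | 3.75 | 33% | 25% | 67% | 60% |
| 1/3 | 1.5 | 4.5 | 40% | 25% | 60% | 50% |
| 50% | 2.0 | 6.0 | 50% | 25% | 50% | 37.5% |

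At d = 10% the ratio is 1/0.9 = 1.11. At d = 30%, assumed composite medians of 2, 4 and 8 months give 6-month Kaplan-Meier values of 23%, 48% and 70%, against 12.5%, 35% and 60% alive without new therapy.

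**Size when deaths are added.** Hold a fixed at ln2/4.5 and let b be 0, a/2 or a. The reported median stays at 4.5 months. The median to next therapy or death, ln2/(a+b), is 4.5, 3.0 and 2.25 months.

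**At the planned size.** Take 20 subjects with first events every half month. The composite median is 5.0 months, and 8/20 = 40% are alive and untreated at 6 months. Censoring 4, 6 or 8 interspersed deaths gives medians of 6.0, 7.0 or 8.0 months and 6-month values of 50%, 53% or 62%. For example, with 4 deaths placed at the 2nd, 6th, 10th and 14th events, the 6-month value is 0.40/[(18/19)(14/15)(10/11)] = 0.498.

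**The case against.** The definition is coherent. TTNT is time to the start of a treatment, and a death is not a start. Censoring deaths is the usual way to describe a cause-specific hazard, and nothing else in the protocol contradicts that reading. This stands, and it means that next therapy or death is a different endpoint, not a correction of the stated one. It does not rescue the output: the section asks for event-free curves and a median as evidence of activity, without saying that they describe a hazard among survivors only.

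Deaths are also not lost from the activity assessment. PFS and duration of response count them, apart from deaths after two or more consecutive missed tumour assessments. Section 5.4 plans no hypothesis tests and no power, and no decision uses TTNT. This stands and limits the weight.

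An analysis plan could add a sensitivity analysis, but the censoring rule is fixed in the protocol itself.

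A reader might infer that more early deaths must lengthen the reported median, so that the endpoint rewards a failing drug. The documents do not support that as a general statement: it needs deaths to replace therapy starts. Nor are the dead carried forward as treatment-free. They leave the risk set, and the flaw lies in what that removal assumes.

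**Conclusion.** The point holds as a minor one. As written, the rule ignores deaths before further therapy. Its curve overstates the proportion alive without new therapy, and its complement overstates the proportion who start it. The direction needs no assumption beyond such deaths occurring.

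The size is conditional. A ratio of 1/(1-d) requires constant hazards and deaths that substitute for therapy starts; with independent, additional deaths the median is unchanged and uninformative about them. Neither d nor any median comes from the protocol. A reader might take the doubling at d = 50% as an expected bias, but a generally poor prognosis does not fix d, so the table shows a range and no forecast. The protocol's description of the population makes a non-zero d plausible and no more.

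**What to change.** Keep the TTNT definition, and in Section 5.5.4 replace the Kaplan-Meier estimate with the cumulative incidence of next DLBCL therapy, treating death from any cause as a competing event (Aalen-Johansen). Show the cumulative incidence of death without further therapy beside it. Alternatively or in addition, report time to next DLBCL therapy or death from any cause by Kaplan-Meier, labelled as that endpoint. In both, censor only living, untreated subjects, at last contact.

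The text change is a sentence or two, and Sections 3.8 and 4.4 already keep subjects in follow-up for next therapy. There are three costs:

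- Death dates must be recorded in that follow-up. The long-term column of Appendix 4 lists only time-to-next treatment and HBV PCR, and routine adverse event reporting under Section 6.2.1 ends 30 days after the last dose or at new anticancer therapy. A missed death matters little as a censoring date, but matters when death is an event or a competing event.
- The composite median will be shorter than the figure from the current rule if deaths move it at all.
- A cumulative incidence may never reach 50% (under constant hazards it levels off at 1-d), so it should be reported at fixed times instead of by a median.
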